### 8.3.5 ADVERSE EVENT REPORTING

In accordance with U-M IRBMED reporting guidelines, moderate and mild AEs that are expected will not be reported to the IRB. Moderate/mild AEs that are unexpected and definitely or possibly related will be reported to the IRB at the time of scheduled continuing review. Moderate AEs that are unexpected and definitely not related will not be reported to the IRB. A summary of AEs will be reported each year to the IRBMED at continuing review. In addition, we will also follow the NIMH Reportable Events Policy and timeline to promptly report these events to the NIMH as required. Safety events requiring expedited reporting will be sent to the) Chair (and forwarded if necessary to the full board) and program office

within 48 hours of notification of the event. A formal report will be submitted to the IRB and NIH within 7 days.

#### 8.3.6 SERIOUS ADVERSE EVENT REPORTING

In accordance with U-M IRBMED reporting guidelines, study-related, life threatening serious adverse event (SAE) reports will be submitted to IRBMED no later than 7 calendar days after learning of the event. If the SAE is expected, it will be reported within 14 days. For SAEs that are not related to the study, reporting will occur at the time of scheduled continuation, or not at all if determined to be expected, per standard reporting timetable of the U-M IRBMED.

#### 8.3.7 REPORTING EVENTS TO PARTICIPANTS

N/A

#### 8.3.8 EVENTS OF SPECIAL INTEREST

N/A

#### 8.3.9 REPORTING OF PREGNANCY

N/A

### 8.4 UNANTICIPATED PROBLEMS

#### 8.4.1 DEFINITION OF UNANTICIPATED PROBLEMS

This protocol uses the definition of Unanticipated Problems as defined by the Office for Human Research Protections (OHRP). OHRP considers unanticipated problems involving risks to participants or others to include, in general, any incident, experience, or outcome that meets all the following criteria:

- Unexpected in terms of nature, severity, or frequency given (a) the research procedures that are described in the protocol-related documents, such as the Institutional Review Board (IRB)-approved research protocol and informed consent document; and (b) the characteristics of the participant population being studied;
- Related or possibly related to participation in the research (“possibly related” means there is a reasonable possibility that the incident, experience, or outcome may have been caused by the procedures involved in the research); and
- Suggests that the research places participants or others at a greater risk of harm (including physical, psychological, economic, or social harm) than was previously known or recognized.

#### 8.4.2 UNANTICIPATED PROBLEMS REPORTING

[name] will report unanticipated problems (UPs) to the reviewing Institutional Review Board (IRB). The UP report will include the following information:

- Protocol identifying information: protocol title and number, PI’s name, and the IRB project number
- A detailed description of the event, incident, experience, or outcome
- An explanation of the basis for determining that the event, incident, experience, or outcome represents an UP

- A description of any changes to the protocol or other corrective actions that have been taken or are proposed in response to the UP

To satisfy the requirement for prompt reporting, UPs will be reported using the following timeline:

- UPs that are serious adverse events (SAEs) will be reported in accordance with description in section 7.6.4.
- Any other UP will be reported to the IRBMED within 14 business days of the investigator becoming aware of the problem.
- All UPs should be reported to appropriate institutional officials (as required by an institution's written reporting procedures), the supporting agency head (or designee), and the Office for Human Research Protections (OHRP) within 7 days of the IRB's receipt of the report of the problem from the investigator.

#### 8.4.3 REPORTING UNANTICIPATED PROBLEMS TO PARTICIPANTS

If there is a UP that directly impacts a participant, they will be informed within 7 days.

### 9 STATISTICAL CONSIDERATIONS

#### 9.1 STATISTICAL HYPOTHESES

As a pilot study, our primary goal is to examine feasibility and acceptability with descriptive data, and we therefore do not have formal hypotheses.

#### 9.2 SAMPLE SIZE DETERMINATION

We will be enrolling 120 participants in the study, including 90 for the pilot feasibility micro-randomized trial. The proposed sample size is not based on detecting an intervention effect but on the goals to determine the acceptability of the intervention components, perceived helpfulness of intervention components (e.g., personalized feedback reports, supportive text messages), and feasibility metrics such as rates of attrition and adherence to study procedures. This number of participants will be sufficient to examine feasibility and acceptability and to explore the range and distribution of outcomes.

#### 9.3 POPULATIONS FOR ANALYSES

Analyses will be conducted using an intent-to-treat approach.

#### 9.4 STATISTICAL ANALYSES

##### 9.4.1 GENERAL APPROACH

For descriptive statistics, categorical and continuous data will be presented via percentages, with ranges, means, and standard deviations when applicable. In keeping with an experimental therapeutics model, we will conduct exploratory analyses comparing the intervention and assessment-only group on the proposed mechanisms (e.g., coping self-efficacy, emotional awareness, readiness to seek-help). We will also be able to utilize multi-level models accounting for repeated assessments to examine associations of intervention components with mechanisms of interest at daily and weekly levels. With 50:50

randomizations for supportive text messages during ~4 week of the 6 weeks, there will be approximately 14 messages (3.5 per week x 4 weeks) for 90 participants, yielding approximately 1,260 next-day outcome datapoints. The six assessment points (five weekly assessments and final follow-up) will also allow for up to 540 outcomes (90 participants x 6 assessments) to compare associations of those randomized to receive PF reports and those who did not receive PF reports on a given week (360 with PF reports vs. 180 without PF). Model diagnostics will be utilized to determine whether corrections for autocorrelation or other model violations are necessary. We will utilize multiple imputation strategies to provide estimates and account for missing data, which is expected in the context of studies with daily assessments. Because pilot studies are not specifically powered for efficacy, we will examine if the pattern of change associated with receiving PF reports and/or supportive text messages are in the desired direction.

---

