### 1.2 SCHEMA

### 1.3 SCHEDULE OF ACTIVITIES

	Screening	Baseline Survey	Weekly (Every Sunday for 5 weeks)	Daily (42 days; Intervention-only)	6-week follow-up (6 th Sunday)
Informed Consent	X				
Demographics	X				
Primary Randomization (Survey Only)		X			
Secondary Randomization (MRT)		X			
Outcome Evaluations					
Flourishing Scale	X		X	*	X
Depression (PHQ-9) and Anxiety (GAD-7)	X		X		X
Coping Self-Efficacy	X		*		X
UCLA-Loneliness Scale	X		X		X
Mental Health Service Utilization	X				X
Pittsburgh Sleep Quality Index-Adapted		X	*		X
Physical Activity (YRBS Adaptation)		X	*		X
Interpersonal Needs Questionnaire (INQ)		X			X
DERS-Emotional Awareness		X	X	*	X
Brief COPE		X			X
National Comorbidity Survey (Suicidal Ideation and Behavior)		X	*		*
Perceived Stress Scale		X	*	*	X
Life Events Checklist (LEC-5)		X			
Readiness for Help-Seeking		X	*		X
Daily Mood				*	
Feasibility/Acceptability Survey					X
Adverse Events Reporting		X			X
Note: X = Full-scale; * = Abbreviated version					

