## 2 INTRODUCTION

### 2.1 STUDY RATIONALE

Depression is the #1 cause of disease-related disability worldwide and prevalence rates for depression and suicide have increased significantly in the United States over the past 25 years. Young adults, including college students, have especially high rates of depression, yet most individuals with clinically significant symptoms do not seek formal treatment. College students at elevated risk for suicide may decline formal treatment due to barriers such as lack of time, low perceived need for treatment, or limited access to services. Mobile health technologies offer promising new opportunities to overcome these barriers and improve outcomes. Further, the use of mobile technologies allows for the gathering of real-time subjective data, and an ability to respond to mood changes directly with an intervention at the time it is needed. Yet, engagement with mobile health interventions tends to wane quickly, and it is unclear how these interventions can best be implemented in ways that promote sustained health benefits. The present study seeks to develop a low-burden mobile intervention that can help first-year college students more readily identify negative trajectories in their mental health and take steps to facilitate effective coping and/or seek formal help. This two-arm pilot study, with an embedded micro-randomized trial (MRT), will allow us to 1) evaluate the feasibility and acceptability of the study intervention components, 2) examine the initial impact of the study intervention components on the proposed mechanisms of change, and 3) through a series of micro-randomizations, inform an adaptive intervention design that provides personalized feedback or text messages only when it is expected to have a positive impact.

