With respect to randomization procedures, we will pre-randomize specific ID numbers and assign numbers sequentially based on completion of the baseline survey, blocking every 20 participants (15 Pilot MRT, 5 Assessment Only) to ensure balance. Those in the Pilot MRT condition will have further randomizations at the weekly level for six weeks, with each week randomized 2:1 to receive a Monday PF report, and each week randomized 2:1 to receive supportive text messages. As an MRT, we will not block for number of weeks receiving each intervention component, and participants may receive different 'doses' of the intervention components over the course of six weeks. Those randomized to receive supportive messages in a given week, as part of the Pilot MRT condition, will have a daily-level 50:50 randomization to receive or not receive a message. If randomized to receive a message on a given day, the message will be randomly pulled from a pool of 25 messages, with each message assigned a numerical value, and this message will be removed from the available pool once it has been received by a given participant. Participants will receive an average of 14 messages over the course of 6 weeks (i.e., ~4 weeks with messages x ~3.5 messages per week). This randomization will allow for the examination of within-person differences for weeks in which a participant is receiving PF reports versus not receiving PF reports, weeks receiving supportive messages versus not receiving supportive messages, between-person differences for volume of messages received at the weekly level, between-person differences for volume of messages or PF reports over the course of six weeks, and short-term (i.e., next-day) within-person changes associated with messages versus not receiving messages.

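### Does Section 9.4.1 leave open which no-message days the next-day text-message comparison uses?

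*Combined protocol and SAP*

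**What the plan says.** Section 9.2 sets the size of the study, "including 90 for the pilot feasibility micro-randomized trial". Section 4.1 describes two layers of message randomisation. Each of six weeks is drawn 2:1 to have messages or not, and participants in a message week "will have a daily-level 50:50 randomization to receive or not receive a message". Sections 6.1.1 and 6.1.2 repeat that the daily draw belongs to message weeks. The Schedule of Activities in Section 1.3 has the daily survey as "Daily (42 days; Intervention-only", so outcomes are collected in off weeks too.

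Section 4.1 lists the contrasts that the design allows. Message weeks against off weeks is one item. A separate item is "short-term (i.e., next-day) within-person changes associated with messages versus not receiving messages".

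Section 9.4.1 opens its count with the 50:50 draws in about four of the six weeks and concludes that "there will be approximately 14 messages (3.5 per week x 4 weeks) for 90 participants, yielding approximately 1,260 next-day outcome datapoints". For the personalised feedback (PF) reports it then gives both sides: "360 with PF reports vs. 180 without PF". Results are to be read by whether "the pattern of change associated with receiving PF reports and/or supportive text messages are in the desired direction". Section 2.1 says that the study will, "through a series of micro-randomizations, inform an adaptive intervention design".

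**The concern.** A contrast has two sides, and Section 9.4.1 counts only one of them for messages, although it counts both for PF reports. The missing side is not automatic under a two-level randomisation. A no-message day can arise from the daily draw inside a message week or from the weekly draw that removed messages for the whole week. The phrase in Section 4.1 fits either set. Section 9.4.3 is marked as not applicable, and Section 9.4.9 does not define the daily contrast.

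Only the same-week days isolate the daily draw. Every message day lies in a message week, whereas half of all no-message days lie in off weeks. A multi-level model fitted to the whole daily file without the weekly assignment would therefore let part of any week-level difference show up as a next-day effect. The plan reads these results by direction and means to use them in designing an adaptive version, so a shift in sign could matter for whether sending on a given day is judged helpful.

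**Working it through.** **Inputs.** Participants in the micro-randomised arm: 90 (Section 9.2). Weeks: 6, with probability 2/3 of being a message week (Section 4.1). Days per week: 7, Monday to Sunday (Section 6.1.1). Probability of a message on a day in a message week: 1/2 (Section 4.1). Daily surveys: 42 per participant (Section 1.3).

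**Reproducing the plan's figure.**
- Message weeks per participant: 6 × 2/3 = 4.
- Messages per participant: 4 × 7 × 1/2 = 14.
- Message days: 90 × 14 = 1,260, as stated.
- The pool of 25 messages barely matters. The chance that a participant draws more than 25 is about 0.8%, and the expected total becomes about 1,259.

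**The other person-days.**
- No-message days in message weeks: 90 × 4 × 7 × 1/2 = 1,260.
- Days in off weeks: 90 × 2 × 7 = 1,260.
- All no-message days: 1,260 + 1,260 = 2,520.
- Total: 1,260 + 2,520 = 3,780 = 90 × 42.
- If day 42 has no next-day survey (an assumption), message-week day-pairs are 90 × 41 × 2/3 = 2,460, or 1,230 on each side. All day-pairs are 90 × 41 = 3,690.

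**PF counts for comparison.** 90 × 6 × 2/3 = 360 and 90 × 6 × 1/3 = 180, as stated. That split is unequal, so giving both sides tells the reader something. Under a 50:50 draw the second side equals the first.

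**Does the choice change the answer?** Simulation with 90 participants, 41 day-pairs, a within-person estimator and 4,000 runs, with no missing surveys. Effects are in residual SD units and all effect sizes are assumed.

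| Assumed truth | Same-week days | All no-message days | All days + weekly assignment |
|---|---|---|---|
| Message weeks lift every day by 0.1, no day effect | 0.000 | 0.038 | 0.000 |
| Message weeks lift every day by 0.2, no day effect | 0.000 | 0.076 | 0.000 |
| Message adds 0.10 next day, halving each day after | 0.097 | 0.113 | 0.097 |
| Message adds 0.10 next day, no carry-over | 0.100 | 0.100 | 0.099 |

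In the first two rows the all-days estimate is positive in 86% and 98% of runs; the same-week estimate is positive in 49–51%. In the last row the all-days estimate is slightly more precise (SD 0.036 against 0.042).

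**Reading the table against the design.** The first two rows need a benefit that is present throughout a message week, even before its first message, while the messages themselves do nothing. The documents describe nothing delivered in message weeks apart from the messages, and PF reports are randomised separately. The third row is the more natural way for a week-level difference to arise. There the readings differ by 0.113 − 0.097 = 0.016 SD and agree in sign.

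**The case for a change.** The strongest case for a change is that the framing in Section 9.4.1 explains how 1,260 messages arise but does not restrict the analysis set. The daily file holds all 3,780 person-days, and the planned multi-level models could be fitted to all of them. Direction is what the plan reads, and direction is what a week-level difference would distort. A single sentence would settle the matter before data are seen.

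Part of this stands. The comparator is implied and not stated, and pooling all 2,520 no-message days without the weekly assignment would mix the two randomisations. But three things limit it. First, Section 9.4.1 plans models at both daily and weekly levels, and Section 4.1 keeps the weekly and next-day contrasts apart, so an analyst following the plan would restrict to message weeks or carry the weekly assignment in the model. Both remove the distortion. Second, the sign-changing result depends on the assumed all-day lift. Third, naming the comparator would not make a direction-only reading informative: with no day effect, the same-week estimate is still positive in about half of runs.

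**Conclusion.** No change is needed. The stated 1,260 is correct as the expected number of outcomes following a sent message, and no rule in the plan is wrong. What is missing is an explicit comparator, and the text already points to the 1,260 no-message days within message weeks. An analyst of a micro-randomised trial would fill this gap in the same way.

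If the other reading were taken, the cost is about 0.016 SD under the assumed carry-over and nothing without carry-over. The larger figures (0.038 and 0.076 SD) are hypothetical, since they assume a week-level lift that the documents give no reason to expect. Section 9.1 states no formal hypotheses, Section 9.2 does not base the sample size on an effect, and the primary outcomes in Section 9.4.2 do not use the daily contrast. All counts are expectations before missing surveys.

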#### 9.4.2 ANALYSIS OF THE PRIMARY ENDPOINT(S)

The primary outcomes include feasibility and acceptability measured by: (1) percentage of eligible participants who agree to participate, (2) percentage of completed follow-ups, (3) number of and reasons for withdrawals, (4) of those randomized to text-messages, percentage of participants who remain active (i.e. do not request to stop messages), (5) visits/clicks for an individual's personalized feedback report page, and (6) participant self-reported satisfaction with the intervention components.

---

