### 5 STUDY POPULATION

#### 5.1 INCLUSION CRITERIA

First-year college students (ages of 17 or above) who are full-time or part-time students enrolled at the University of Michigan, Ann Arbor or Flint campuses with mild-to-moderate depressive symptoms, and who are not receiving professional mental health services will be eligible to participate. Students who may be eligible will first be identified through the university's administrative database. Depressive symptoms and current treatment-seeking status will be verified via email administered questionnaires, after obtaining informed consent from interested students.

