## 5.5 STRATEGIES FOR RECRUITMENT AND RETENTION

We will send out an e-mail to a randomized batch of approximately 2,500 students (2,000 UM-Ann Arbor, 500 UM-Flint), provided by the respective student registries, inviting them to complete an initial 8-minute survey. We anticipate approximately 425 (17%) will consent to participate and complete the **screening** survey, and that 142 (33%) will screen as eligible (mild-to-moderate depression symptoms as defined by PHQ-9 score of 5-14; no current MH treatment) for the intervention portion of the study. The screening survey will be administered to all invited participants and takes approximately 8-10 minutes to complete. After initially sending out the screening survey, we will also send two follow-up reminders via email a couple days apart to remind potential participants of the opportunity to participate in the study. Our full sample will be recruited in this ~10-day period.

We anticipate 120 students (85%) will continue to this next phase of the study, provide a cell-phone number, and complete the **baseline** survey (all within this same Qualtrics flow as the screening survey). Once the baseline survey has been completed, participants will be randomized 3:1 to a “Assessment Only” (n = 30) or “Intervention” (n=90) condition. Based on student enrollment and screening rates from a prior study, we anticipate our sample to be 67% female, 63% White, 20% Asian, 9% Black, 8% Multi-racial, and 12% Hispanic.

Our research group has developed several successful strategies to improve participant retention. For completion of the baseline survey, daily and weekly assessment surveys, and final follow-up survey we will provide participants with financial compensation in the form of a re-loadable digital Visa card. For the initial completion of the screening survey, participants will be entered into a drawing for one of ten \$50 digital Visa cards. For completion of the baseline survey, participants will receive \$20. For daily surveys, participants will receive \$1 for each completed survey. For weekly assessments, participants will receive \$10 for each completed survey. Finally, participants will receive \$25 for completing the final, 6-week follow-up survey. Participants will have payments issued each week based on the number of completed surveys.

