### 8 STUDY ASSESSMENTS AND PROCEDURES

## 8.1 ENDPOINT AND OTHER NON-SAFETY ASSESSMENTS

To recruit participants, we will obtain e-mail addresses of 2,500 first-year undergraduate students from the registrar (2,000 randomly selected from UM-Ann Arbor, and 500 from UM-Flint, which reflects the full annual enrollment of first-year undergraduate students at the UM-Flint campus) and invite them to participate in an 8-minute survey screen of their mental health, with an online consent form. We anticipate approximately 425 students will consent to participate and complete the **screening survey**, and that 142 students will meet criteria for a positive screen of mild-moderate depressive symptoms (PHQ-9 score of 5-14) and no current psychotherapy for the intervention portion of the study. We anticipate that 85% of the 142 participants who screened eligible for the study will continue to this next phase of the study, provide a cell-phone numbers, and complete the **baseline survey** (all within the same Qualtrics flow of the screening survey). The screening survey will be administered to all invited participants who consent to participate and takes approximately 8 minutes to complete. It will be sent out on a Tuesday, with reminders on Friday, and following Monday. Participants are deemed eligible if they score 5-14 on the PHQ-9, denoting mild-to-moderate depressive symptoms **and** report they are not currently enrolled in a form of mental health care (e.g., therapy). The baseline survey will be administered to participants screening positive on the screen, when they provide their cell phone number, and takes 10-15 additional minutes to complete. Randomization (3:1 to intervention versus assessment-only) occurs after baseline survey has been completed. Daily surveys will be administered to participants in the intervention group only, and take approximately 1 minute to complete, with links to the survey texted at 8pm each day. Weekly surveys are administered to all participants on Sunday evenings and take approximately ten minutes to complete. The final follow-up survey takes approximately 25 minutes to complete and will be administered to all randomized participants (n=120) on their sixth Sunday of the project. Administration of all surveys will be conducted via an online, automated system (Qualtrics).

[figure not shown]

Figure 1. Enrollment Flowchart

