**Primary Outcomes:** The primary outcomes include feasibility and acceptability measured by: (1) percentage of eligible participants who agree to participate, (2) percentage of completed follow-ups, (3) number of and reasons for withdrawals, (4) of those randomized to text-messages, percentage of participants who remain active (i.e. do not request to stop messages), (5) visits/clicks for an individual's

personalized feedback report page, and (6) participant self-reported satisfaction with the intervention components. Participants' feedback will be obtained with Likert scale items and open-ended questions, including overall perspective on personalized feedback reports, and receiving text messages, experience (e.g., ease of accessing intervention components, acceptability of intervention timing, frequency, and duration), and recommended changes.

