##### 10.1.1.2 CONSENT PROCEDURES AND DOCUMENTATION

Participants will be invited via e-mail to participate in the study and be provided with an electronic consent form that can be viewed and downloaded. Participants will be informed of the general nature of the study, expectations for their participation, the voluntary nature of their participation, the risk/benefits, limitations to confidentiality, and that they may withdraw from the study at any time. As a digital study, formal written consent will be waived and participants will be required to attest that they have reviewed the consent form and wish to participate prior to proceeding to the screening survey. A waiver for parental consent will be obtained so that 17-year-old first-year college students may participate in the study.

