#### 10.1.6 SAFETY OVERSIGHT

While we are specifically targeting students with mild-to-moderate symptoms of depression, there may be students whose symptoms worsen over the course of the study (as we would expect among first-year college students, regardless of study participation). Participants reporting suicidal thoughts in Qualtrics surveys will receive an immediate response including crisis hotline telephone numbers and the local Psychiatric Emergency Department.

As the PI, [name] will ensure that all relevant University of Michigan IRBMED policies, procedures, and stipulations are being followed. He will be responsible for ensuring that research staff adhere to the IRBMED policies, including: 1) all participants will understand and agree to an electronic consent form before participating; 2) all participants will be provided with a copy of the informed consent; 3) strict adherence to participant's right to withdraw or refuse to answer any questions will be maintained; 4) the assessments will be completely confidential and no names will be associated with the assessment data; 5) identifying information will be kept separate from the actual participant data; 6) all identifying information will be locked/saved with passwords on secure servers; 7) participants will be informed in writing in the consent form how to contact the PI and IRB office with any questions or concerns.

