#### 10.1.7 CLINICAL MONITORING

Study monitoring will be conducted to ensure that the rights and well-being of participants are protected, that the reported data are accurate, complete, and verifiable, and that the conduct of the study is in compliance with the protocol and with applicable regulatory requirements. [name] will be responsible for monitoring the data safety and quality. All research projects involving human participants require approvals from the University of Michigan Medical School's Institutional Review Board (IRBMED). Annual reviews will be conducted by IRBMED, including the number of subjects screened, enrolled, and withdrawn. The IRB will also review protocol deviations, adverse events, and complaints that arise in connection with the study. As the PI, [name] will ensure that all relevant IRBMED policies, procedures, and stipulations are being followed.

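### Does primary measure 1, the share of eligible students who agree to take part, leave the recruitment result undefined or misleading?

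*Combined protocol and SAP*

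**What the plan says.** Sections 8.1 and 9.4.2 list the same six primary measures. Section 9.4.2 begins: "The primary outcomes include feasibility and acceptability measured by: (1) percentage of eligible participants who agree to participate". The others are completed follow-ups, withdrawals, staying active on text messages, visits to the feedback page, and satisfaction. No numerator event or denominator is spelled out for the first.

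The order of events is given elsewhere. Section 5.1: "Depressive symptoms and current treatment-seeking status will be verified via email administered questionnaires, after obtaining informed consent from interested students". Section 10.1.1.2: "participants will be required to attest that they have reviewed the consent form and wish to participate prior to proceeding to the screening survey". Consent therefore comes before the screen, and the screen comes before eligibility is known.

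Section 5.5 then describes a further step for those who screen eligible: "We anticipate 120 students (85%) will continue to this next phase of the study, provide a cell-phone number, and complete the" baseline survey. Randomisation follows that survey.

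Section 9.1 says feasibility and acceptability are examined descriptively, without formal hypotheses. Section 9.2 sets the enrolment target at 120.

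**The concern.** There are two apparent faults. First, every student in the denominator has already consented and completed a survey, so measure 1 cannot reflect how many invited students ignore the e-mail. The other five measures all concern stages after enrolment. In a feasibility pilot, the largest expected loss would then sit outside the primary outcomes, and a weak response could leave measure 1 looking healthy.

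Second, the word *agree* is not tied to an event. In its list of the investigator's duties, Section 10.1.6 says that "all participants will understand and agree to an electronic consent form before participating". If agreeing meant accepting the consent form, measure 1 would be 100% by construction, because nobody can be found eligible without having consented.

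Flint seemed to sharpen the point. Section 8.1 says of its 500 invitations: "which reflects the full annual enrollment of first-year undergraduate students at the UM-Flint campus". A poor response there could not be made up by further Flint invitations in the same intake.

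**Working it through.** **Inputs** (Sections 4.1, 5.5 and 8.1): 2,500 invited; 425 consent and complete the screen (17%); 142 eligible (33%); 120 complete the baseline and are randomised (85%).

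**The plan's own figures.**
- 2,500 × 0.17 = 425.
- 425 × 0.33 = 140.3, against 142 stated; 142/425 = 33.4%.
- 142 × 0.85 = 120.7, against 120 stated; 120/142 = 84.5%.

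The chain reproduces within rounding. End to end it is 120/2,500 = 4.8%.

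**Where the loss falls.** Total 2,500 − 120 = 2,380.
- Before the screen is complete: 2,500 − 425 = 2,075 (87.2%).
- Ineligible at the screen: 425 − 142 = 283 (11.9%).
- Eligible but not continuing: 142 − 120 = 22 (0.9%).

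Measure 1 can see only the 22. But 2,075 and 22 are not like for like: the 22 are all eligible, while the 2,075 are a mixture. If non-responders were eligible at the screeners' rate (an assumption), 2,075 × 0.334 ≈ 693 would be eligible and about 1,382 would not. If 10% to 50% of them were eligible (an assumed range), the number runs from 208 to 1,038. The early loss of eligible students is larger on any of these values, but it cannot be observed, because eligibility is never established for non-responders.

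**The two readings of *agree*.**
- Accepting the consent form: 142/142 = 100%, whatever happens.
- Completing the baseline and being randomised: 120/142 = 84.5%.

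Only the second varies with the data, and Section 5.5 itself attaches a percentage to that step with the eligible students as denominator. For the earlier step, Sections 4.1, 5.4, 5.5 and 8.1 speak of consenting, and Section 5.4 separates consenting from entering the study.

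**Would a poor response be hidden?** Randomised = 2,500 × r × (142/425) × (120/142), with the later rates held fixed.
- r = 17%: 120.
- r = 10%: 250 screened, 83.5 eligible, 70.6 randomised.
- r = 5%: 125 screened, 41.8 eligible, 35.3 randomised.

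Measure 1 is 84.5% each time, but enrolment falls short of 120 by about 49 and 85. Any report that gives the number randomised shows that.

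**Flint**, assuming equal rates on both campuses: 500 × 0.048 = 24 randomised at 17% response, and 500 × 0.10 × 0.334 × 0.845 = 14.1 at 10%. The plan states no campus target. Ann Arbor's 2,000 invitees are a random selection; the size of the pool they come from is not given.

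**The case for a change.** The best case for a change is that a pilot meant to inform a later trial should fix its recruitment rates in advance. The plan's wording for consenting and for agreeing is close, the later step is called continuing and is never linked to measure 1, and an undefined event lets a favourable denominator be chosen afterwards. Response is also the likely limit on enrolment, since recruitment lasts about 10 days and screen failures are not re-screened. Definitions would cost one clause and a small table.

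The factual core of this stands: the event is not named, the denominator is conditional on consent and screening, and no primary measure covers the response to the e-mail. The inference to a needed change does not. Sections 3 and 4.1 put the objective as feasibility and acceptability of the intervention and its components, and Section 9.2 refers to attrition and adherence; nowhere is recruitment by e-mail an objective in its own right. Making the response rate a primary outcome is therefore a preference.

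Nor does the information depend on such a change. The invitation list is known, the screen and baseline are counted by the survey system, and Section 10.1.7 adds: "Annual reviews will be conducted by IRBMED, including the number of subjects screened, enrolled, and withdrawn". Section 8.1 also has an enrolment flowchart; the figure is not reproduced in the text available, so its stages could not be checked.

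Two neighbouring points, the unstated denominator for satisfaction and the Section 3 cells that name a survey time point as the endpoint, are separate wording matters. Section 4.1 confines the added acceptability items to the intervention arm, and measure 2 reports follow-up completion.

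**Conclusion.** No change is needed. This is a gap that analysts fill sensibly. Read with Section 5.5, measure 1 is the proportion of screen-eligible students who complete the baseline and are randomised, planned at 120/142 = 84.5%. It is a valid rate for that step so long as it is described as conditional on prior consent and screening. It says nothing about the 17.0% response (425/2,500), which a competent report would give beside it as a descriptive recruitment figure. The overall 4.8% (120/2,500) would be recruitment yield rather than acceptance, since it includes ineligible students.

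The conclusion rests on three things: the Section 5.5 reading of *agree*, which is the only informative one; the outcomes being descriptive, so that no test or estimate turns on the definition; and the number randomised being reported against the target of 120, which would expose a poor response. The shortfall figures assume that eligibility and continuation stay at the planned 33.4% and 84.5%.
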